6.1.2 Minor Changes

- Section 8 of the protocol only discusses an estimand and intercurrent events related to the primary objective. The estimand framework has been built in Section 9.0 of this SAP for all the secondary objectives related to estimation of the treatment effect.
- Section 8.4.6 of the protocol describes a summary of abnormal physical examination findings should be presented. During the review of the initial SAP draft, the study team decided that a listing of all findings would be sufficient.
- Section 8.4.6 of the protocol also describes discrepancies between randomisation stratification information (obtained from IRT) and strata formed based on Screening factor collected on eCRFs (HPV status) will be explored. The HPV status on the CRF Randomisation page is integrated from the IRT data and so this presentation isn't necessary.
- Section 8.4.6 of the protocol also describes a presentation of modified World Health Organisation (WHO) ratings. These ratings are not collected for this study, hence no presentations will be provided.
- Section 8.2 of the protocol define the PK analysis set as "...all patients who receive at least 1 dose of setanaxib and have at least 1 measured concentration at a scheduled PK time point post-dose." A clarification was added to note that any concentration below the quantification limit (BQL) is considered to be a measured concentration and therefore included.

6.1.3 Clarifications

- The protocol uses "Major" as well "Important" to describe significant protocol violations. The SAP will use "Important" to align with ICON standard terminology.
- The protocol describes that the Per-Protocol Analysis Set (PPS) will include all patients in the FAS who
 complied sufficiently with the protocol with respect to exposure to IMP, availability of tumour assessments,
 and absence of important protocol deviations likely to impact efficacy outcome. These components are assed
 manually in the review of the deviation log, and the flag labelled "Impact to Primary Endpoint (Y/ N)" will be
 solely used for excluding subjects from the PPS. See Section 9.2.4 for details.
- The protocol uses terms for both "patient" and "subject", this SAP will use "patient" throughout.

• The protocol uses "IMP or placebo" whilst the eCRF uses "IMP" to refer to setanaxib/placebo. This SAP will use IMP in the same way as the eCRF, to mean setanaxib/placebo.

7.0 Study Objectives and Endpoints

7.1 Primary Objective and Endpoint

Primary Objective	Primary Endpoint
• To compare the change in tumour size per Response Evaluation Criteria in Solid Tumours Version 1.1 (RECIST v1.1) in recurrent or metastatic SCCHN patients treated with setanaxib and pembrolizumab versus patients treated with placebo and pembrolizumab	 Best percentage change in tumour size, defined as the best percentage change from Baseline in the sum of diameters of target lesions (TLs), as assessed by RECIST v1.1

7.2 Secondary Objectives and Endpoints

Key Secondary Objectives	Key Secondary Endpoints
• To compare the progression-free survival (PFS) per RECIST v1.1 in recurrent or metastatic SCCHN patients treated with setanaxib and pembrolizumab versus patients treated with placebo and pembrolizumab	 PFS, defined as time from randomisation to the first documented disease progression per RECIST v1.1 or death due to any cause, whichever occurs first. PFS at 3, 6, and 12 months and median PFS will be summarised
• To compare the change from Baseline in CAFs level in tumour tissue from recurrent or metastatic SCCHN patients treated with setanaxib and pembrolizumab versus patients treated with placebo and pembrolizumab	Change from Baseline in CAFs level in tumour tissue
• To compare the change from Baseline in the number of CD8 ⁺ TILs and regulatory T-cells in tumour tissue from recurrent or metastatic SCCHN patients treated with setanaxib and pembrolizumab versus patients treated with placebo and pembrolizumab	 Change from Baseline in the number of CD8⁺TILs and regulatory T-cells in tumour tissue
Other Secondary Objectives	Other Secondary Endpoints
• To assess the overall response rate (ORR), the DoR and disease control rate (DCR) per RECIST v1.1 in recurrent or metastatic SCCHN patients treated with setanaxib and pembrolizumab versus patients treated with placebo and pembrolizumab	 Proportion of the patients who have a complete response (CR) or partial response (PR) per RECIST v1.1 will be used to assess ORR The minimum time when CR or PR is first observed to the time of progression of disease (PD) or death will be used to assess DoR Proportion of the patients in whom the best overall response is determined as CR, PR, or stable disease (SD) per RECIST v1.1 will be used to assess DCR
To assess the overall survival (OS) in recurrent or metastatic SCCHN patients treated with setanaxib and pembrolizumab versus patients treated with placebo and pembrolizumab	 OS, defined as the time from Randomisation to death due to any cause. Patients without documented death at the time of the final analysis will be censored at the date of the last follow- up.
To evaluate the safety and tolerability profile of setanaxib and pembrolizumab, versus placebo and pembrolizumab, in recurrent or metastatic SCCHN patients	 AEs: monitoring for AEs at all visits Adverse events of special interest (AESIs):

	o Anaemia
	 Hypothyroidism
	Vital signs:
	o Pulse rate
	 Systolic blood pressure (SBP)
	 Diastolic blood pressure (DBP)
	12-lead electrocardiogram (ECG): clinically significant abnormalities
	Physical examination: abnormal findings
	Laboratory tests:
	 Haematology
	o Biochemistry
	∘ Urinalysis
	 Thyroid function test
To compare the change from Baseline in PD-L1 expression in tumour tissue from recurrent or metastatic SCCHN patients treated with setanaxib and pembrolizumab versus patients treated with placebo and pembrolizumab	Levels of PD-L1 expression in tumour tissue
• To compare the change from Baseline in patterns of gene expression and differential gene expression in tumour tissue from recurrent or metastatic SCCHN patients treated with setanaxib and pembrolizumab versus patients treated with placebo and pembrolizumab, using Ribonucleic acid (RNA) sequencing	 Gene expression quantification and analysis of patterns of gene activation for CAFs and CD8⁺ TILs, and regulatory T-cells
 To assess the plasma exposure of setanaxib and its metabolite GKT138184 	 Pre-dose and post-dose plasma concentrations of setanaxib and GKT138184: Area under the concentration-time curve over the last 24-h dosing interval at steady state (AUC[0-24]-ss) Minimum plasma concentration at steady state (Cmin.ss)
	 Maximum plasma concentration at steady state (Cmarss) Maximum plasma concentration at steady state (Cmarss)

7.3 Exploratory Objectives and Endpoints

Exploratory Objectives		Expl	loratory Endpoints
•	To assess the relationship between setanaxib and GKT138184 plasma exposure and response, if data permits	•	Where data permit, the pharmacokinetics (PK) (setanaxib and GKT138184 plasma exposure)/pharmacodynamics (e.g., changes in biomarkers, efficacy, and safety parameters) relationship may be explored graphically and/or using appropriate PK/pharmacodynamic modelling techniques
•	To compare the change from Baseline in patterns of gene expression and differential gene expression in tumour tissue from recurrent or metastatic SCCHN patients treated with setanaxib and pembrolizumab versus patients treated with placebo and pembrolizumab, using RNA sequencing	•	Gene expression quantification and analysis of patterns of gene activation for relevant immuno-oncology, inflammatory, and other relevant gene signatures
•	To compare changes in circulating biomarkers detectable in peripheral blood in recurrent or metastatic SCCHN patients treated with setanaxib and pembrolizumab versus patients treated with placebo and pembrolizumab	•	Evaluations of pre-, on-treatment, and progression peripheral blood samples for circulating biomarkers which may include but will not be limited to panels of cytokines, chemokines and other soluble biomarkers; T-cell receptor repertoire analysis; and analysis of gene expression biomarkers associated with immunomodulatory effects

8.0 Study Design

This is a randomised, double-blind, placebo-controlled, proof-of-concept, Phase 2 study assessing setanaxib coadministered with pembrolizumab in patients with recurrent or metastatic SCCHN. The safety and efficacy of setanaxib 800 mg BID will be assessed against matching placebo over up to 105 weeks of treatment. The design is depicted in Figure 1.

AE=adverse event; CAFs=cancer-associated fibroblasts; IV=intravenously; PFS=progression-free survival; PO=per os (orally, or via either a feeding tube or a percutaneous endoscopic gastrostomy device in case patients are unable to swallow tablets); q3w=every 3 weeks; R=randomisation; RECIST v1.1=response evaluation criteria in solid tumours version 1.1 * For patients with a suitable archival tumour biopsy sample available, the archival sample may be used to assess CAFs level and determine eligibility (Note: this can only be performed after the patient has provided signed informed consent). This will not dispense from the need for a recent pre-study tumour biopsy.

The study plans to randomise approximately 50 patients at up to approximately 35 investigational centres in North America and Europe, to the IMP, according to a 1:1 randomisation ratio, stratified by HPV status. Depending on the number of patients providing evaluable Week 9 biopsy and imaging data, up to an additional 20 patients (making a maximum of 70 patients) may be randomised to ensure an adequate amount of data is available for the efficacy and biomarker analyses.

The study will consist of an up to 35-day Screening Period, an up to 24-month Treatment Period (Day 1 to Week 105), and a 28-day Safety Follow-up Period. The total duration of the study for patients remaining in the study until their final follow-up assessment will be up to approximately 114 weeks (approximately 2 years and 2 months).

All patients included in this study will receive pembrolizumab, with setanaxib or placebo given as add-on therapy to a recognised and approved standard-of-care agent.

Treatment with pembrolizumab will continue until: RECIST v1.1-defined disease progression is determined by the investigator (Eisenhauer et al 2009), unacceptable toxicity, or a maximum of 24 months. If progression is suspected, but not confirmed, study treatment may continue until confirmation of radiological progression. Treatment with setanaxib or placebo will continue throughout the period of pembrolizumab therapy. When pembrolizumab is discontinued, blinded study treatment will also be discontinued.

Baseline assessments will be performed on Day 1 (Visit 2). Post-Baseline assessments will be performed every 3 weeks up to pembrolizumab discontinuation. Following permanent IMP discontinuation at any time during the study, patients will undergo an End-of-Treatment (EoT) Visit as soon as possible and a Safety Follow-up Visit at 28 days after the last dose.

Initial tumour imaging is performed within 35 days prior to the date of treatment and will be used as the Baseline scan for the tumour assessments. Tumour assessments will then be conducted from the date of randomisation and continue until RECIST v1.1-defined disease progression, irrespective of treatment discontinuation. Efficacy Follow-up for PFS and survival will continue until approximately 38 progression events have occurred. AEs will be recorded up to 28 days after study treatment discontinuation, while any further anti-cancer medication will be recorded until disease progression.

The primary endpoint is best percentage change in tumour size. A population with measurable disease will be selected to generate the maximum tumour response data. The secondary endpoints related to numbers of CAFs, CD8⁺ TILs, and regulatory T-cells in tumour tissue, and gene expression analysis in tumour tissue will be used to demonstrate the underlying mechanisms of action of setanaxib and support the primary objective.

Safety and tolerability data will be regularly reviewed by an unblinded IDMC, with the first assessment after approximately 12 patients (6 per treatment group) have had the opportunity to complete at least one cycle of pembrolizumab +/- setanaxib, followed by periodic assessments at a frequency defined in the IDMC Charter. The IDMC may recommend changes to the setanaxib dose regimen or study conduct based on the safety data reviews.

After approximately 12 patients (6 per treatment group) have completed their Baseline and post-treatment biopsy, initial gene expression and biomarker data in tumour tissue may be reviewed by the sponsor, who will be unblinded to randomised treatment assignment, although subject IDs will remain masked. A second review may be performed, if required.

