8 STATISTICS

8.1 General Procedures

The statistical analysis will be performed by ICON under the direction of Calliditas.

With the exception of the unblinded statistician and programmers supporting the IDMC, all personnel involved with the analysis of the study will remain blinded until database lock and identification of protocol deviations. Analyses will be performed using SAS[®] (SAS Institute, Cary, NC, US) by the sponsor or its representatives.

A detailed description of all statistical analyses to be performed for this study and any deviations from the analysis detailed in the protocol will be outlined in the statistical analysis plan (SAP). A first version of the SAP will be prepared prior to the inclusion of the first study patient, and the SAP will be approved prior to database lock and unblinding of the study data.

All data will be presented by treatment group. For qualitative variables, the population size (N for sample size and n for available data) and the percentage (of available data) for each class of the variable will be presented. Quantitative variables will be summarised using descriptive statistics, including n, mean, standard deviation (SD), median, minimum, and maximum values. Graphical presentations of the data will be produced to aid interpretation.

Baseline is defined as the last nonmissing measurement before or on the date of first administration of IMP, unless otherwise stated in the SAP.

A strategy for dealing with data affected by protocol deviations will be agreed by the study sponsor physician, pharmacokineticist and statistician prior to database lock. Data from patients who discontinue from the study, or who have missing values for other reasons, will be included in the analysis in such a way as to minimise any possible bias.

An initial data cut-off will occur approximately 9 weeks after completion of enrolment, when all patients are expected to have had at least 3 cycles of pembrolizumab, at least one post-treatment scan, and the opportunity for a post-treatment tumour biopsy. At this point, the primary endpoint of best percentage change in tumour size and some secondary endpoints will be analysed. An updated analysis may be performed after 38 progression events have been reported. During ongoing review of the overall progression event count, if the predicted timing of the initial and updated analyses are expected to be close in proximity, one analysis may be performed.

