Investigators and patients will continue to be blinded to randomised study treatment after initial unblinding of data for the primary analysis until the final database lock.

Safety and tolerability data will be regularly reviewed by an unblinded IDMC, with the first assessment after approximately 12 patients (6 per treatment group) have had the opportunity to complete at least 1 cycle of pembrolizumab +/- setanaxib. Safety data analyses will be descriptive only and will be described in the SAP and IDMC charter.

After approximately 12 patients (6 per treatment group) have completed their Baseline and post-treatment biopsy, initial gene expression and biomarker data in tumour tissue may be reviewed by the sponsor, who will remain masked to randomised treatment assignment. A second review may be performed, if required. Analyses will be descriptive only. Further details will be provided in the SAP.

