8.3 Blinding

The investigator, the site personnel, the sponsor and their representatives involved in monitoring and conducting the study, and the patients will be blinded to treatment assignments.

The randomisation lists containing the true treatment assignment and kit lists containing the IMP kit assignments of patients will be maintained by ICON IRT system and ALMAC Clinical Services respectively. This information will not be accessible to any blinded project team members prior to the primary analysis, nor to the investigators or patients prior to updated analysis.

Additional details regarding the unblinding process can be found in the Data Blinding and Documentation Plan for further details.

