11.2 Sponsor Review of Gene Expression and Biomarker Data

The Sponsor will conduct an interim review of initial gene expression and biomarker data in tumour tissue. This will occur after approximately 12 patients (6 per treatment group) have completed their Baseline and post-treatment biopsy. The review will be performed by personnel who are not part of the main study team. For further details, please refer to the standalone Biomarker Analysis Plan.

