12.0 Statistical Methods

With the exception of the unblinded statistician and programmers supporting the IDMC, all personnel involved with the analysis of the study will remain blinded until the initial database soft lock at the time of the primary analysis. Further details on the blinding and unblinding are given in the study Blinding Plan.

In this study, it is planned to recruit approximately 35 investigational centres in USA and Europe. Unless specified otherwise, data from all participating sites will be combined for the analysis, so that an adequate number of patients will be available for analysis. In the event that a single site enrols a large proportion of patients, a site effect may be explored as described in Section 12.5.5, otherwise no site effect will be assessed.

All table summaries will be presented by treatment group (including an overall group for safety tables) and by analysis visit where appropriate. Unscheduled visits will be windowed as described in Section 10.4. Unscheduled visit values will contribute to any assessment of worst/most severe results, but otherwise will only be displayed in listings. Additional details related to specific presentations are given in programming notes of the supporting TFL shells.

Categorical variables will be summarised descriptively using counts and percentages. Percentages will be rounded to one decimal place, except 100%, which will be displayed without any decimal places and percentages will not be displayed for zero counts.

Continuous variables will be summarised using univariate statistics, including the number of observations (n), mean, standard deviation, median, minimum and maximum. The minimum and maximum values will be displayed to the same level of precision as the raw data, the mean and median to a further decimal place and the standard deviation to two additional decimal places. In addition, for tumour and biomarker summaries, the geometric mean and the interval of (geometric mean +/- geometric standard deviation) may also be presented.

Analyses will be performed using SAS® (SAS Institute, Cary, NC, US) version 9.4 or higher.

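### SAP 8.0 unblinds the sponsor without limit at the 12-patient biomarker review, and the restriction in SAP 11.2 is not carried into 8.0 or 12.0

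*SAP*

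**What the plan says.** SAP 8.0 (Study Design) provides for a look at tumour gene-expression and biomarker data once about 12 patients, 6 per arm, have paired biopsies. The reviewer is the sponsor, "who will be unblinded to randomised treatment assignment, although subject IDs will remain masked". A second look is allowed.

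The supplied protocol (version 4.0, 25 April 2023) describes the same review in its Summary, Section 3.1 and Section 8.1. Each time the reviewer is the sponsor, "who will remain masked to randomised treatment assignment".

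Other SAP sections that bear on this:

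- 8.3 (Blinding): "the sponsor and their representatives involved in monitoring and conducting the study, and the patients will be blinded to treatment assignments". On the randomisation and kit lists it adds: "This information will not be accessible to any blinded project team members prior to the primary analysis".
- 11.2 (Sponsor Review of Gene Expression and Biomarker Data): "The review will be performed by personnel who are not part of the main study team". Detail is left to a standalone Biomarker Analysis Plan.
- 12.0 (Statistical Methods) sets this rule for the time up to the soft lock for the primary analysis: "With the exception of the unblinded statistician and programmers supporting the IDMC, all personnel involved with the analysis of the study will remain blinded".
- 6.1 (Changes from Protocol): major changes, minor changes and clarifications are listed. None concerns the masking of this review.

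**The concern.** In a double-blind trial, the plan should let a reader say exactly who knows treatment assignment, and from when. Here 8.0, 11.2 and 12.0 give three different answers for one review. Taken literally, 8.0 gives the whole sponsor by-arm results while the trial is running.

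The data are not incidental. SAP 8.1 says that CAFs, CD8+ TILs, regulatory T-cells and tumour gene expression will decide proof of concept, and all but gene expression are key secondary endpoints. The sponsor also keeps influence after the review:

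- Under SAP 6.0, an initial SAP version is signed before the biomarker look, and a final version goes to the sponsor for approval later.
- Under SAP 12.4, the sponsor joins the case-by-case review of deviations affecting the primary endpoint. Under 9.2.4, that flag alone decides who leaves the per-protocol set, on which the primary analysis is repeated (12.5).

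By-arm knowledge ahead of those steps could influence them, or appear to.

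**Working it through.** The plan gives no figure to reproduce on this point. The check is a comparison of texts, plus one proportion.

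**1. Who may be unblinded at the review**

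| Place | Reviewer or group covered | Treatment known? |
|---|---|---|
| Protocol v4.0: Summary, 3.1, 8.1 | Sponsor | No |
| Protocol v4.0, 8.1 | Analysis personnel, except IDMC support | No, until database lock |
| SAP 8.0 | Sponsor, no limit stated | Yes, patient IDs masked |
| SAP 8.3 | Sponsor staff who monitor or conduct the study | No |
| SAP 11.2 | Sponsor review by people outside the main study team | Not stated |
| SAP 12.0 | Analysis personnel, except IDMC support | No, until soft lock for primary analysis |

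**2. SAP 8.0 against the supplied protocol.** These are opposites on the same review. Protocol 8.1 also keeps analysis staff blinded, "all personnel involved with the analysis of the study will remain blinded until database lock and identification of protocol deviations", with the same single exception for IDMC support.

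**3. SAP 8.0 against SAP 12.0.** The only exception in 12.0 is the statistician and programmers serving the IDMC. Someone must attach treatment codes to the biomarker data and tabulate them by arm. That is analysis work, and 12.0 has no exception for the people who do it or for those who read the result. This conflict lies within the SAP and does not depend on the protocol version.

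**4. SAP 8.0 against SAP 8.3.** Section 8.3 covers sponsor staff who monitor or conduct the study, and withholds the lists from team members who are blinded. A separate unblinded sponsor group is compatible with that wording. So 8.3 does not contradict 8.0 when 8.0 is read with 11.2, but it does not mention the review either.

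**5. What SAP 11.2 restricts.** It restricts who sits on the review. It does not say what those people may do afterwards, who prepares their data, or whether by-arm results may pass to the study team.

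**6. Declaration.** SAP 6.1.1 to 6.1.3 go down to points of terminology but have no entry for this change.

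**7. Share of the trial at the first review.** Patients reviewed: about 12 (SAP 8.0, 11.2). Planned size: 50, up to 70 (SAP 8.0).

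- 12 / 50 = 0.24, or 24%
- 12 / 70 = 0.171, or 17%

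This describes how much is seen. It does not measure bias.

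**The case against.** The best case for the plan is that 11.2 is the operative section and 8.0 only a summary. Section 11.2 states a firewall outright, 8.3 fits with it, and 12.0 speaks of people involved in analysing the study, which reviewers outside the team might not be. Access rules may be in the Biomarker Analysis Plan or the blinding plan, neither supplied. The SAP is written against protocol version 5.0 (12 December 2023). If that version dropped the masking, there is no departure and nothing to list in 6.1. Exposure is also limited: the review concerns biomarkers, not the primary endpoint; sites and patients stay blinded; an initial SAP is signed beforehand; the stated ground for adding up to 20 patients is the number with evaluable Week 9 data; and the updated analysis is tied to about 38 progression events.

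Much of this stands. The 8.3 point is right, the version point is open, and an access list may exist. Two things remain. Other documents cannot cure an SAP whose sections disagree on who is unblinded, and 12.0 leaves no place for those who prepare the by-arm data. And 11.2 is a single sentence on membership, silent on later roles and on the flow of results.

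A reader might go further and infer that the people who see by-arm data also decide on sample size, SAP content or timing of analyses. The documents do not show this: they do not say who makes the sample-size and timing decisions, and 11.2 points the other way. A reader might also infer that individuals could be recognised from 6 patients per arm. Nothing says that reviewers receive biopsy dates or other identifying detail.

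**Conclusion.** The point holds as an inconsistency that should be corrected. SAP 8.0 followed as written gives an unspecified sponsor group by-arm data on proof-of-concept endpoints, at 24% (of 50) or 17% (of 70) of planned enrolment for the first review. The limit in 11.2 is missing from 8.0 and 12.0, and nothing separates the reviewers from later SAP approval or deviation review.

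The conflict between 8.0 and 12.0 rests on the SAP alone, on the reading that preparing or reviewing by-arm data counts as involvement in the analysis. The conflict with the protocol and the gap in 6.1 rest on version 4.0 and must be confirmed against version 5.0. It would be too strong to say that the SAP departs from its governing protocol, or that its blinding section forbids the review. Nor do the documents show that the review took place or that it biased anything, and they give no basis for calculating a bias.

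**What to change.** Choose one of two routes and make SAP 8.0, 8.3, 11.2 and 12.0 agree.

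1. **Masked review**, as in protocol version 4.0: delete the unblinding clause from 8.0.
2. **Unblinded review behind a firewall:**
   - Carry the 11.2 restriction into 8.0.
   - Name the reviewers, by role, and those who prepare their data as an exception in 8.3 and 12.0.
   - State that they take no part in sample-size, SAP, deviation or analysis-timing decisions.
   - State that they do not pass by-arm results to the study team.

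On either route, check protocol version 5.0. If it still requires masking and route 2 is kept, enter the change and its reason in SAP 6.1.1.

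The cost is a few sentences in the SAP, matching text in the blinding plan and an access list. Protocol 6.2 already requires unblinded staff to be documented, so the list should be little extra work. Sample size, endpoints and analyses are unchanged.
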